6.2.3. Vital Signs

Triplicate vital signs measurement will be taken at pre-dose only. Single supine blood pressure, oral temperature, and pulse rate measurements will be taken at times detailed in the Schedule of Activities given in the protocol.

Baseline will be defined as the mean of the replicated pre-dose (0 hours) measurement on Day 1.

The following vital signs endpoints will be determined:

- Change from baseline in supine systolic and diastolic blood pressure, oral temperature and pulse rate.
- The maximum decrease and increase from baseline over all measurements taken post-dose for supine systolic and diastolic blood pressures, oral temperature and pulse rate.

The maximum increase from baseline will be calculated by first subtracting the baseline value from each post-dose measurement to give the change from baseline. The maximum of these values over the respective period will then be selected, except in the case where a subject does not show an increase. In such an instance, the minimum decrease should be taken.

Similarly, the maximum decrease from baseline will be determined by selecting the minimum value of the changes from baseline. In cases where a subject does not show a decrease, the minimum increase should be taken.

6.2.4. ECG and Telemetry

ECG

A single 12-lead ECG will be obtained on all subjects at screening and follow-up.

12-lead ECGs will be recorded in triplicate on all subjects at all other time points as detailed in the Schedule of Activities given in the protocol.

The QT, heart rate, QTcF, PR, RR and QRS will be recorded at each assessment time.

If not supplied, QTcF will be derived using Fridericia's heart rate correction formula:

$$QTcF = QT / (RR)^{1/3} \quad \text{where } RR = 60/HR \text{ (if not provided)}$$

The average of the triplicate readings collected at each assessment time will be calculated for each ECG parameter. Baseline will be defined as the average of the triplicate pre-dose recordings collected at 0 hours on Day 1.

The maximum absolute value (post-dose) and the maximum increase from baseline for QT, heart rate, QTcF, PR and QRS, will be determined over the first 24 hours post-dose for Day 1, and also over all measurements taken post-dose for QTcF, PR and QRS.

The maximum increase from baseline will be calculated by first subtracting the baseline value from each post-dose measurement to give the change from baseline. The maximum of these values over the respective period will then be selected, except in the case where a subject does not show an increase. In such an instance, the minimum decrease should be taken.

Changes from baseline for the ECG parameters QT interval, heart rate, QTcF interval, PR interval, and QRS interval will also be calculated.

Telemetry

All abnormal rhythms will be recorded and reviewed by the study physician for the presence of rhythm of potential clinical concerns, which will document the time, duration and description of the clinically significant event.

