4. STUDY DESIGN

4.1. Overall Design

This is a Phase 1, randomized, double-blind, Sponsor-open, placebo -controlled, first-in-human single -ascending dose study to evaluate the safety, tolerability, and PK of PF-06755347 in healthy adult male participants by IV and SC administration and in male or female participants with persistent or chronic ITP by SC administration. Personnel, trained in advanced cardiac life support, emergency resuscitative equipment and the management of anaphylaxis, are immediately available to treat systemic reactions under the supervision of a physician. IV fluids, epinephrine, antihistamine and methylprednisolone will be available for immediate parenteral use in the event of an anaphylactic reaction.

A schematic of the overall study design is provided in [Section 1.2](#) (note actual dose levels to be administered beyond the starting dose are subject to change, see [Section 4.2.1.3](#)). A total of approximately 75 healthy adult male participants are planned to be randomized to either receive PF-06755347 or placebo by intravenous or subcutaneous administration in a 3:1 allocation ratio. All participants with ITP will receive PF-06755347. Clinical data from the IV cohorts supporting the transition to SC dosing are summarized in the IB, Section 6. SC Cohorts 7-14 are planned, Cohort 7 will have 4 male participants (3 active and 1 placebo)

and Cohorts 9-11 will have 8 male participants (6 active and 2 placebo). Cohort 12 (optional Japanese cohort) will include approximately 4-8 male Japanese healthy participants and Cohorts 13 and 14 combined will include a maximum of 12 male or female participants with ITP. The total number of participants randomized will not exceed 87. The ITP cohort dosing will start after completion of the 50 mg dose cohort in HPs.

Participants within each cohort will be dosed using a sequential dosing scheme. For all cohorts, only a single participant will be dosed at any given time. Based on the emerging safety data to date with IV dosing, cytokine and laboratory abnormalities reach their peak levels within the first few hours following PF-06755347 C_{max} and are resolved within 24 hours. The C_{max} was predicted to be 24 -48 hours with SC administration, however preliminary data from Cohort 7 supports increasing the monitoring period to 96-hr for safety.

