4.2.1.3.2. Subcutaneous Administration in Healthy Participants

Following IV administration of PF-06755347, the observed safety data to date has shown Grades 1 and 2 CRS associated with IV doses of 1.0 and 0.7 mg/kg, respectively. Cytokine (eg, IL-6) elevation peaked within the first few hours following IV administration and returned to baseline levels within 24 hours. These results may suggest that the degree of cytokine release is dose dependent and potentially correlated with PF-06755347 C_{max} and the rate of rise to achieve C_{max} . SC dosing of PF-06755347 offers the potential to blunt the severity of CRS by reducing the C_{max} and delaying the time to achieve C_{max} (T_{max}). The observed C_{max} (0.895 $\mu\text{g/mL}$) at the proposed starting SC dose of 25 mg is approximately 5-fold lower than the observed mean C_{max} (4.7 $\mu\text{g/mL}$) achieved at the highest tolerated IV dose level of 0.3 mg/kg ([Table 6](#)), with a safety margin of 1263 for C_{max} and 345 for AUC_{168} . Observed C_{max} values in subsequent dose levels of 50 and 100 mg were of 1.37 and 2.64 $\mu\text{g/mL}$ respectively; approximately 3.5-fold and 1.8-fold lower than the values observed at the 0.3 mg/kg IV dose level. The SC dose level of 300 mg will only be explored when SC doses up to 200 mg levels are deemed to be safe and well tolerated and within the PK stopping limit criteria.

In order to support subcutaneous delivery of PF-06755347, a toxicology study (Study 14MA141, IB Section 5.3.7) in NHP was conducted with a single 250 mg/kg SC dose and the results showed that the drug was tolerated.

The dose for the optional Japanese SC Cohort 12, if conducted, will be the highest dose from Cohorts 7-11 that is found to be safe and well tolerated.

Table 7. Observed/Predicted Human Exposures and Safety Margins Following Single SC Administration of PF 06755347

Dose (mg) ^a	Human Exposure of Plasma PF-06755347		Safety Margin ^b	
	C _{max} (µg/mL)	AUC ₅₇₆ or AUC ₁₆₈ (SC) (µg·hr/mL)	C _{max}	AUC
25 mg SC ^c	0.895	98.5	1263	345
50 mg SC ^c	1.37	159	825	214
100 mg SC ^c	2.64	315	428	108
200 mg SC	5.28	630	214	54
300 mg SC	7.92	945	143	36

- Depending on the safety and PK data available, dose escalation may be adjusted to doses other than those outlined above while following dose progression and stopping rules outlined in [Section 6.6](#) and [Section 6.7](#).

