9.8. Safety Analysis

Adverse events, ECGs, BP, pulse rate, pulse oximetry, continuous cardiac monitoring by telemetry, and safety laboratory data will be reviewed and summarized on an ongoing basis during the study to evaluate the safety of participants. Any clinical laboratory, ECG, BP, pulse rate or oxygen saturation abnormalities of potential clinical concern will be described. Safety data will be presented in tabular and/or graphical format and summarized descriptively, where appropriate.

Medical history and physical examination information, as applicable, collected during the course of the study will be considered source data and will not be required to be reported, unless otherwise noted. However, any untoward findings identified on physical examinations conducted during the active collection period will be captured as an AE, if those findings meet the definition of an AE. Data collected at Screening that is used for inclusion/exclusion criteria, such as laboratory data, ECGs and vital signs will be considered

source data, and will not be required to be reported, unless otherwise noted. Demographic data collected at Screening will be reported.

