‡ Low-flow nasal cannula or facemask is defined as oxygen delivered at ≤ 6 L/min. Low flow also includes blow-by oxygen delivery, sometimes used in pediatrics. High-flow nasal cannula or facemask is defined as oxygen delivered at > 6 L/min. This is modified from original ASTCT criteria to differentiate between low-flow and high-flow facemask.

Abbreviations: ASTCT = American Society for Transplantation and Cellular Therapy; BiPAP = bilevel positive airway pressure; CPAP = continuous positive airway pressure; CRS = cytokine release syndrome; CTCAE = Common Terminology Criteria for Adverse Events.

CRS identification and management (adapted from Neelapu et al¹³)

- Monitor vital signs (temperature, blood pressure, pulse and SpO₂) according to SoA and at a minimum, every 1 hour until vital signs have returned to baseline levels. If clinical symptoms suggestive of CRS are reported by the participant outside of the scheduled windows of the SoA, close monitoring of vital signs should be conducted as above.

Fever (body temperature $\geq 38.0^{\circ}\text{C}$)

- Acetaminophen/paracetamol and cooling blanket for the treatment of fever.
- Non-steroidal anti-inflammatory drugs (NSAIDs) such as ibuprofen/naproxen can be used as second treatment option for fever if not contraindicated.
- Assess for infection using blood and urine cultures and nasal swab for COVID-19 as indicated.
- Initiate oral or IV fluids for hydration as tolerated. Increase fluid rate from the existing IV catheter.

Hypotension (Systolic Blood Pressure < 90 mmHg or a decrease of 20% from baseline levels in either systolic or diastolic blood pressure whichever is lower).

- IV fluid 500 ml of normal saline given as rapidly as the existing safety IV cannula can tolerate.
- May give a second 500 ml of normal saline if participant remains hypotensive or participant's symptoms of hypotension do not resolve.

Corticosteroid Use:

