2. INTRODUCTION

PF-06755347 is a recombinant human IgG1 multimeric Fc fusion protein which includes the IgG1 hinge region, the CH2, and CH3 domains, with a human IgG2 hinge domain fused onto the C terminus. The molecule is designed to form Fc multimers, in order to enhance avidity to Fc γ receptors (Fc γ Rs).

The current study is the first clinical trial proposed with PF-06755347. It is designed to evaluate the safety, tolerability, pharmacokinetics (PK), as well as potential pharmacodynamic (PD) effect of PF-06755347 following single intravenous (IV) doses of PF-06755347 to healthy adult subjects.

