Appendix 1. Categorical Classes for ECG and Vital Signs of Potential Clinical Concern

Categories for QTcF

| | | | |
|----------------------------------|------------------|------------------|------------|
| QTcF (ms) | 450 < max. ≤ 480 | 480 < max. ≤ 500 | max. > 500 |
| QTcF (ms) increase from baseline | 30 < max. ≤ 60 | max. > 60 | |

Categories for PR and QRS

| | | |
|---------------------------------|--|--|
| PR (ms) | max. ≥ 300 | |
| PR (ms) increase from baseline | Baseline > 200 and max. ≥ 25% increase | Baseline ≤ 200 and max. ≥ 50% increase |
| QRS (ms) | max. ≥ 140 | |
| QRS (ms) increase from baseline | ≥ 50% increase | |

Categories for Vital Signs

| | | |
|---|--------------------|--------------------|
| Systolic BP (mm Hg) | min. < 90 | |
| Systolic BP (mm Hg) change from baseline | max. decrease ≥ 30 | max. increase ≥ 30 |
| Diastolic BP (mm Hg) | min. < 50 | |
| Diastolic BP (mm Hg) change from baseline | max. decrease ≥ 20 | max. increase ≥ 20 |
| Supine pulse rate (bpm) | min. < 40 | max. > 120 |

Measurements that fulfill these criteria are to be listed in report.

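### The SAP keeps IV-era safety outputs: ECG heart-rate and uncorrected-QT maxima stop at 24 h, and temperature and SpO2 have no counts at the protocol's own limits

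*SAP*

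**What the plan says.** **Design covered.** SAP section 2 describes the study as evaluating the drug "following single intravenous (IV) doses of PF-06755347 to healthy adult subjects". SAP section 1 records no amendments. Protocol 2.1 now says that IV dosing has ended and that SC dosing continues, including in participants with ITP.

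**ECG maxima.** SAP 6.2.4 says that the maximum and maximum increase of five ECG measures (heart rate, PR, QRS, uncorrected QT, QTcF) "will be determined over the first 24 hours post-dose for Day 1, and also over all measurements taken post-dose for QTcF, PR and QRS".

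**Timing.** Protocol 4.2.1.3.2 reports that cytokine "elevation peaked within the first few hours following IV administration". For SC dosing, Protocol 4.1 says Cmax "was predicted to be 24 -48 hours with SC administration" and adds that "preliminary data from Cohort 7 supports increasing the monitoring period to 96-hr for safety".

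**Categories.** SAP Appendix 1 has rows for QTcF, PR, QRS, systolic and diastolic pressure, and pulse rate. It counts systolic <90 mmHg or a fall of at least 30. In the row "Diastolic BP (mm Hg) change from baseline" it counts a fall of at least 20, with a separate row for diastolic <50. It has no row for temperature or SpO2.

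**Protocol side.** Section 9.8 says "Adverse events, ECGs, BP, pulse rate, pulse oximetry, continuous cardiac monitoring by telemetry, and safety laboratory data will be reviewed and summarized", and that oxygen-saturation abnormalities of potential concern will be described. Section 3 lists body temperature among the primary endpoints. Appendix 10 uses 38.0 °C for fever, SpO2 below 94% as its hypoxia trigger, and for hypotension a systolic pressure under 90 or "a decrease of 20% from baseline levels in either systolic or diastolic blood pressure whichever is lower".

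**The concern.** Cytokine release syndrome (CRS) at the higher IV doses is what ended IV dosing, and its objective signs are fever, low blood pressure and low oxygen saturation. A 24 h window suits a 1 to 3 h infusion. After an SC dose it closes as the predicted peak begins. The planned tables give no count of participants who reached 38.0 °C or fell below 94% saturation, and the blood-pressure rows use different limits from the protocol's CRS appendix.

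Protocol 4.1 puts 3 active participants in Cohort 7 and 6 in each of Cohorts 9–11, and Table 4 puts 3 to 6 in each ITP cohort. One affected participant is therefore 1/6 = 17% to 1/3 = 33% of a dose group, so a count is more informative than a mean.

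**Working it through.** The plan states no sample size, power or error rate for these outputs, so there is no figure to reproduce. The check compares windows and thresholds.

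**1. Windows after dosing**

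| Measure | Maximum over 24 h | Maximum over all post-dose times |
|---|---|---|
| QTcF, PR, QRS (SAP 6.2.4) | yes | yes |
| ECG heart rate, uncorrected QT (SAP 6.2.4) | yes | no |
| Pulse rate, blood pressure, temperature (SAP 6.2.3) | – | yes |

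The SC schedules continue ECGs beyond 24 h, so the data for the two missing entries exist. For uncorrected QT this also touches a stated output: Protocol 9.8.1 asks for the number of participants with corrected and uncorrected QT of at least 500 msec, with no 24 h limit, while SAP 8.3.7 lists such values for QTcF only.

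**2. Temperature and SpO2**

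SAP 8.3.6 summarizes and plots temperature and its change, but its counts and its listing of values of concern depend on Appendix 1, which has no temperature row. Change from baseline does not recover the count. As an illustration, a rise of 1.5 °C gives 36.2 + 1.5 = 37.7 °C from one baseline and 36.8 + 1.5 = 38.3 °C from another.

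SpO2 is not among the SAP's safety endpoints (6.2), its vital signs (6.2.3) or its categories. At most it falls under SAP 6.2.5, which lists additional data if they reach the database. That is less than Protocol 9.8 promises.

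**3. Blood pressure**

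For baseline b, a fall of exactly 20% is counted by the SAP if:

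- systolic: 0.2b ≥ 30 (b ≥ 150), or 0.8b < 90 (b < 112.5);
- diastolic: 0.2b ≥ 20 (b ≥ 100), or 0.8b < 50 (b < 62.5).

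Within the protocol's normal range (90–139 and 50–89, section 8.2.2), whole-number baselines of 113–139 systolic (27 of 50) and 63–89 diastolic (27 of 40) leave such a fall uncounted for that pressure. Example: 120/75 to 95/59 is 25/120 = 20.8% and 16/75 = 21.3%. It meets no row, since 25 < 30, 95 ≥ 90, 16 < 20 and 59 ≥ 50.

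The missed band is narrow. It is widest at a systolic baseline of 120 (falls from 24 to just under 30 mmHg; 30/120 = 25%) and at a diastolic baseline of 70 (14 to just under 20 mmHg; 20/70 = 28.6%). Above 25% systolic or 28.6% diastolic, every fall is counted at any baseline.

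**4. How many falls this would affect**

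The documents give no baseline distribution, so these are assumptions: normal baselines truncated to the protocol's normal range.

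- *Falls of exactly 20%, systolic (SD 10):* uncounted 24% at mean 105, 41% at 110, 60% at 115, 77% at 120, 95% at 130. At mean 120: [Φ(2) − Φ(−0.75)] / [Φ(2) − Φ(−3)] = 0.751/0.976 = 77%.
- *Falls of exactly 20%, diastolic (SD 8):* 42% at mean 60, 83% at 70, 98% at 80.
- *All falls of 20% or more, size uniform from 20% to 40%:* 6–14% uncounted systolic (means 110–125), 21–26% diastolic (means 68–78).
- *The same, with sizes bunched just above 20% (exponential excess, mean 5 points):* 18–41% systolic, 49–62% diastolic.

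**5. The wording of the 20% limit**

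The closing words of the Appendix 10 definition can mean the lower of the two limits. The systolic limit would then be min(90, 0.8b), never above 90, and the SAP's <90 row would already cover it.

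**The case against.** The strongest reply is that most of this ground is covered elsewhere. SAP 6.2.3 takes pulse-rate maxima over every post-dose measurement, and SAP 8.3.6 counts pulse above 120 at scheduled and unscheduled times alike. SAP 8.3.7 summarizes changes in heart rate and QT and plots them by participant. QTcF, the interval used in the categorical tables, has both windows. This stands, and it limits the ECG gap to two maxima.

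On blood pressure, absolute mmHg limits are a legitimate choice, and <90 and <50 match the protocol's normal range. The 20% limit sits in CRS management guidance and is ambiguous. This also stands in part. However, Protocol 6.6 names hypotension and hypoxia as pause events and refers to Appendix 9, whose table grades only vomiting and diarrhea. Appendix 10 is therefore where the numeric hypotension limit is found, and it bears on more than management.

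A reader might draw three stronger conclusions, and the documents support none of them:

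- *That most falls at the protocol limit go uncounted.* This needs a baseline distribution and a distribution of fall sizes, and the answer changes with both.
- *That entry criteria guarantee a 20% fall never reaches the SAP change limits.* The 140/90 cap applies at screening, up to 56 days before dosing. The SAP baseline is the Day 1 pre-dose mean, for which no cap is stated.
- *That CRS detection rests on investigator reports alone.* Each participant's data are reviewed before the next is dosed, CRS grade has its own CRF, and systolic <90 is already tabulated.

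**Conclusion.** The concern holds in a limited form.

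- **Timing:** maxima for ECG heart rate and uncorrected QT end at 24 h, the start of the 24–48 h predicted for SC Cmax and well short of the 96 h SC safety review. No other maximum is affected. This rests on the predicted time of Cmax; the protocol text gives no observed SC Tmax.
- **Temperature and SpO2:** this is the firmest part, because it needs no assumption. A primary endpoint has no count at the protocol's fever limit, and pulse oximetry has no planned summary although Protocol 9.8 promises one.
- **Blood pressure:** a narrow band is missed, for falls of about 20% at baselines of roughly 113–139 systolic or 63–89 diastolic. Its systolic part disappears under one reading of Appendix 10.

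The study is descriptive, so no inference is at risk, and real-time safety review does not depend on these tables. What is at stake is whether the final report shows the objective signs of the known dose-limiting risk at the protocol's own limits. The sponsor reporting standards that the SAP cites are not available here and might add some of these outputs.

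**What to change.** - **SAP 6.2.4:** take maximum and maximum increase for ECG heart rate and QT over all post-dose measurements as well as 24 h, as is already done for QTcF, PR and QRS.
- **SAP Appendix 1 and 8.3:** add the number and percentage of participants with any post-dose temperature of 38.0 °C or higher, and with any post-dose SpO2 below 94%, labelled as measurement counts and not as CRS diagnoses. Summarize SpO2 by treatment and time, as Protocol 9.8 states.
- **Blood pressure:** keep the existing rows; systolic <90 needs no addition. The sponsor should clarify the closing words of the hypotension definition in Protocol Appendix 10 and reconcile it with SAP Appendix 1, then add one count at the reconciled limit. Which limit is right is for the sponsor to decide.

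The cost is a few extra table rows and one clarification of wording. All the data are already collected, and nothing existing is removed.

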6.2.5. Other Safety Data

Additional safety data will be collected as described in the protocol and will be listed if collected in the sponsor's database.

6.3. Pharmacokinetic Endpoints

Blood samples for PK analysis of PF-06755347 will be taken according to the Schedule of Activities given in the protocol.

The following PK parameters will be calculated for PF-06755347 from the concentration-time values using standard non-compartmental methods:

Table 1. Non-compartmental PK Parameters

| Parameter | Analysis Scale | PF-06755347 |
|----------------------------|----------------|-------------|
| C_{\max} | ln | D |
| C_{\max} (dn) | ln | D |
| T_{\max}^* | R | D |
| $t_{1/2}^*$ | R | D |
| AUC_{last} | ln | D |
| AUC_{last}^* (dn) | ln | D |
| AUC_{inf}^* | ln | D |
| AUC_{inf}^* (dn) | ln | D |
| CL^* | ln | D |
| V_{ss}^* | ln | D |

Key: A=analyzed using statistical model, D=displayed with descriptive statistics, ln=natural-log transformed, R=raw (untransformed), *=if data permits

6.4. PD Endpoints

None.

CCI

[REDACTED]

6.6. Other Endpoints

6.6.1. Immunogenicity (ADA)

Response rates of the development of anti-PF-06755347 antibodies (ADA).

Definitions for positive ADA will be determined with the completion of the validation work for the assay and may be included in an amendment to this SAP prior to final database lock.

6.7. Covariates

None.

7. HANDLING OF MISSING VALUES

For the analysis of safety endpoints, the sponsor data standard rules for imputation will be applied.

7.1. Concentrations Below the Limit of Quantification

In all data presentations (except listings), concentrations below the limit of quantification (BLQ) will be set to zero. (In listings BLQ values will be reported as “<LLQ”, where LLQ will be replaced with the value for the lower limit of quantification). For PK calculations, BLQ will be handled by the Pfizer standard processes.

